3.1.1.2 Imputation for adverse event start dates

The following imputation rules apply to cases in which the start date is incomplete (ie, partial or completely missing) for adverse events.

In addition to the following rules, if the stop date is complete and the imputed start date is after the stop date, then the start date will be imputed using the stop date. If the stop date is present and implies that the adverse event (AE) is treatment-emergent (ie, stop date is on or after the date of first dose of IP in the study), but the start date is completely missing, then the start date will be imputed with the date of first dose of IP. If the stop date is present and does not imply that the AE is treatment-emergent (ie, stop date is prior to the date of first dose of IP in the study), but the start date is completely missing, then the start date will be imputed with the stop date.

For start dates with missing day and month (year is present):

- If the year of the incomplete start date is the same as the year of the date of the first dose of IP, then the day and month of the date of the first dose of IP will be assigned to the missing fields.
- If the year of the incomplete start date is prior to the year of the date of the first dose of IP, then December 31 will be assigned to the missing fields.

- If the year of the incomplete start date is after the year of the date of the first dose of IP, then January 1 will be assigned to the missing fields.

For start dates with missing month only (day and year are present):

- The day will be treated as missing and both month and day will be replaced according to the above procedure.

For start dates with missing day only (month and year are present):

- If the month and year of the incomplete start date are the same as the year and month of the date of the first dose of IP, then the date of the first dose of IP will be assigned to the missing day.
- If either the year of the incomplete start date is before the year of the date of the first dose of IP or if both years are the same but the month is before the month of the date of the first dose of IP, then the last day of the month will be assigned to the missing day.
- If either the year of the incomplete start date is after the year of the date of the first dose of IP or if both years are the same but the month is after the month of the date of the first dose of IP, then the first day of the month will be assigned to the missing day.

For incomplete time in start date

- Note that when dates are recorded using time (from 00:00 until 23:59) and if time is missing in a start date record, time = 00:01 will be assigned; if time is missing in a stop date record, then time = 23:59 will be assigned.

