- p. Spirometry measurements will be done at -1 h and -15 min pre-dose and then 15 min, 30 min, 1, 2, 4, 8, 12, 23, and 23:45 hours post-dose on Visits 3, 5, 6, 8, 9 and 11. At Visits 4, 7 and 10 spirometry measurements will be done at -1 h and -15 min pre-dose and at 15, 30 min, 1, 2, and 4 hours post-dose.
- q. Cough VAS will be done pre-dose at Visits 3, 4, 6, 7, 9, and 10, and 24 hours post-dose at Visits 5, 8, and 11.
- r. Cough monitoring will be done starting 24 hours prior to dosing on Visits 3, 6, and 9, and pre-dose at Visits 5, 8, and 11. The recording for Visits 3, 6 and 9 are home recordings and will start at least 24 hours before the dosing and will finish pre-dose. Cough monitoring for Visits 5, 8 and 11 will start on Day 14, just before dosing at site, and will finish 24 hours later. Patients may attend the site between visits to collect the cough monitor prior to the recording start.
- s. All patients will receive ipratropium (20 µg × 2 puffs 4 times per day) during the run-in and wash-out periods. In addition, those patients that were taking any LAMA and/or LABA will be maintained with ipratropium between Visit 1 and Visit 2. Ipratropium should be held at least 8 hours before Visits 3, 6 and 9 (before any pulmonary function test) and during all treatment periods (until last pulmonary function test at Visits 5, 8 and 11).
- t. Inhaler training will be done before starting IP treatment on Day 1 at each treatment period.
- u. The first dose of IP is to be taken at the clinic at 9:00 AM±2 hours on Day 1 of each treatment period (Visits 3, 6 and 9) after the pre-dose specified procedures (and randomisation for Visit 3). On subsequent days of each treatment period, IP is to be taken within ±1 hour of dosing time of Day 1 (and between 7 AM and 11 AM). IP administration will be at the site on Day 1, 2, 8 and 14 of each treatment period. This will be supervised at the clinic. Day 3 to Day 7 and Day 9 to Day 13 of each treatment period - doses will be taken at home.

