8.3.4 Adverse event data collection

The following variables will be collect for each AE:

- AE (verbatim).
- The date and time when the AE started and stopped.
- Maximum intensity.
- Whether the AE is serious or not.
- Investigator causality rating against the IP(s) (yes or no).
- Action taken with regard to IP(s).
- AE caused patient's withdrawal from study (yes or no).
- Outcome.

In addition, the following variables will be collected for SAEs:

- Date AE met criteria for serious AE.
- Date Investigator became aware of serious AE.
- AE is serious due to.
- Date of hospitalisation.
- Date of discharge.
- Probable cause of death.
- Date of death.
- Autopsy performed.
- Causality assessment in relation to study procedure(s).
- Causality assessment to other medications.

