9.4.2 Safety analyses

All demographic and baseline characteristics, safety outcomes and other variables will be analysed using the safety population.

Safety will be assessed by descriptive analysis of AEs, vital signs, ECGs and clinical laboratory assessments.

All analyses of safety and tolerability outcomes will be performed on the safety population. Individual safety and tolerability data will be provided in data listings and summarised as appropriate by treatment. Continuous variables (laboratory parameters [including i-STAT], vital signs and ECG) will be summarised using descriptive statistics (n, mean, SD, minimum, median, and maximum) as appropriate by scheduled assessment time point. Where applicable, data will be summarised for the observed value, and for the corresponding change from baseline/screening. Categorical variables will be summarised in frequency tables (counts and percentage). Change from baseline will be calculated as the differences between the post-dose value at each time point and the morning value prior to administration of the IP.

For all variables, 12-lead ECG parameters, vital signs and laboratory tests (including i-STAT), baseline values will be defined as the values obtained prior to the morning IP administration on Day 1 of Visit 3.

Any clinically relevant new physical examination findings or worsening of a pre-existing physical examination finding that were to be recorded as an AE will be presented with the AEs.

AEs: The number and percentage of patients who experienced 1 or more treatment-emergent AEs (TEAEs), and the number of TEAE occurrences will be tabulated by treatment group. Adverse events occurring before administration of IP (ie, not treatment-emergent) and the number of occurrences will be reported in the same way as TEAEs. An AE will be considered a TEAE if it was not present prior to the date of the first dose of IP or was present prior to the date of the first dose of IP, but increased in severity after IP administration. A TEAE that

occurs during a wash-out period will be associated to the last treatment taken. An AE that occurs more than 42 days after the last IP administration will not be counted as a TEAE. TEAE tables will be tabulated by system organ class, preferred term, intensity, causality, action taken, outcome, seriousness criteria and treatment group using descriptive statistics.

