3.5 Safety variables

3.5.1 Adverse events

AEs: The number and percentage of patients who experienced 1 or more treatment-emergent adverse event (TEAE), and the number of TEAE occurrences will be tabulated by treatment group. An AE is considered TEAE if the event occurs after first dose of IMP up to 42 days after the administration of the last dose of IMP or was present prior to the date of the first dose of IP, but increased in intensity after IP administration. All events present before first IMP are considered non-TEAEs.

Adverse events occurring before administration of IP (ie, not treatment-emergent) and the number of occurrences will be reported in the same way as TEAEs in a different Table.

A TEAE that occurs during a wash-out period will be associated to the last treatment taken. An AE that occurs more than 42 days after the last IP administration will not be counted as a TEAE.

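### The SAP's 00:01 default for a missing AE start time falls before the Day 1 dose, and no rule says whether treatment-emergence is judged by date or by date and time

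*SAP*

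**What the plan says.** **Imputed time.** SAP 3.1.1.2 covers adverse events with an incomplete start: "if time is missing in a start date record, time = 00:01 will be assigned". It has no separate rule for dosing days. Protocol 8.3.4 lists among the collected items "The date and time when the AE started and stopped", so recorded times are expected.

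**Imputed date.** The same SAP section moves a partial start date onto the first-dose date when its known parts match. It does likewise when the start date is wholly missing and the stop date falls on or after the first dose. In doing so it explains treatment-emergence by comparing dates.

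**Dosing time.** Protocol 1.1, Table 1, footnote u: "The first dose of IP is to be taken at the clinic at 9:00 AM±2 hours on Day 1 of each treatment period".

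**Treatment-emergence in the SAP.** SAP 3.5.1: "An AE is considered TEAE if the event occurs after first dose of IMP up to 42 days after the administration of the last dose". It adds: "All events present before first IMP are considered non-TEAEs". SAP 4.4.1.1 likewise treats events before the first dose as non-treatment-emergent and keeps them out of the AE summary tables.

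**Treatment-emergence in the protocol.** Protocol 9.4.2: "An AE will be considered a TEAE if it was not present prior to the date of the first dose of IP". SAP section 6, which lists changes from the protocol, does not mention this definition.

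**Attribution.** SAP 3.5.1: "A TEAE that occurs during a wash-out period will be associated to the last treatment taken".

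**The concern.** One minute past midnight on a Day 1 is always earlier than the planned dose. An event that began after the first inhalation but has no recorded time would therefore be placed before it, if the SAP's dose-based wording is applied to date and time. The imputation would then work against itself: one rule brings an incomplete date onto the first-dose date, where it counts as treatment-emergent, and the next sets a time that takes it out again.

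Safety and tolerability is a stated objective, and the AE tables are read by treatment. Protocol 2.3 names palpitations, headache and tremor for beta-2 agonists, and cough and upper-airway irritation for inhaled antimuscarinics. If such effects appear soon after a first inhalation, Day 1 is where they would be recorded. In a crossover, an event taken from the treatment just started may also be added to another treatment. Two programmers could follow this SAP correctly and produce different tables.

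**Working it through.** The plan gives no figure on this point, so the check is clock arithmetic followed by a comparison of the two possible rules.

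**Step 1: gap between the default and the dose.** Inputs: 00:01 (SAP 3.1.1.2) and a dose at 07:00 to 11:00 (Protocol Table 1, footnote u).

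- 07:00 − 00:01 = 6 h 59 min
- 09:00 − 00:01 = 8 h 59 min
- 11:00 − 00:01 = 10 h 59 min

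**Step 2: days from the previous period's last dose to 00:01 on the next Day 1.** This matters because events more than 42 days after the last dose are not treatment-emergent, and the wash-out is 42 to 49 days. With a wash-out of *w* calendar days and a previous last dose at hour *h*:

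elapsed days = *w* − (*h* − 1/60)/24

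| Wash-out | *h* = 7 | *h* = 9 | *h* = 11 |
|---|---|---|---|
| 42 days | 41.709 | 41.626 | 41.542 |
| 43 days | 42.709 | 42.626 | 42.542 |
| 49 days | 48.709 | 48.626 | 48.542 |

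Only the 42-day wash-out stays within the limit. From 43 days on, the result depends on whether the limit runs from each period's last dose or from the last dose of the whole study. The documents do not say.

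**Step 3: status of a Day 1 event with no recorded time.**

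| Where Day 1 falls | Dates compared | Date and time compared |
|---|---|---|
| Period 1 | Treatment-emergent, treatment just started | Non-treatment-emergent |
| Periods 2 and 3, 42-day wash-out | Treatment-emergent, treatment just started | Treatment-emergent, previous treatment |
| Periods 2 and 3, 43 to 49 days | Treatment-emergent, treatment just started | Previous treatment if the limit runs from the last dose of the study; non-treatment-emergent if it runs from each period's last dose |

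In the right-hand column, no untimed Day 1 event is counted under the treatment started that day, whichever treatment it is.

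**Step 4: incomplete dates.** A start record with a missing day will usually lack a time too. Once placed on the first-dose date it receives 00:01 and, by date and time, precedes the dose. Reading the first dose as the first in the study, as that section words its own test, this concerns Period 1 only.

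**Step 5: comparison with medications.** SAP 3.1.1.1 has the same 00:01 default for concomitant medication. It does no harm there, because SAP 3.2.3 counts by date and expressly includes the first-dose date. SAP 3.5.1 has no such wording for adverse events.

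**The case against.** The strongest defence is that status is meant to be judged by date. Protocol 9.4.2 says so. SAP 3.1.1.2 tests treatment-emergence by date, as does the part of SAP 3.5.1 on events that worsen after dosing. SAP section 6 declares no change. On that reading the 00:01 default has no effect on the AE tables. SAP 3.1.1.3 also links imputed times to AE duration, for which an early start and a late stop are a normal choice. This stands as a plausible reading, and it rules out any claim that misclassification is certain. It does not settle the matter. The duration sentence sits in the section on stop dates and does not confine the start-time rule to that use. "An AE is considered TEAE if the event occurs after first dose of IMP" is also naturally read by the clock when times are both collected and imputed.

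The second defence is size. Start times are collected, and Day 1 is a supervised overnight stay, so missing times may be few. Nor would an affected event vanish: SAP 3.5.1 provides a separate table for events before dosing, and SAP 4.4.1.1 keeps them in listings. Both points stand and keep the matter minor.

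**Conclusion.** The default is wrong as written, with minor severity. Under the SAP's own dose-based wording it gives the wrong status to an untimed post-dose Day 1 event, and the SAP does not say whether date or date-time governs. The consequence depends on date and time being compared. The number of affected events is unknown and may be small or nil.

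Three stronger inferences are tempting, and the documents support none of them:

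- **That every untimed Day 1 event will be misclassified.** Under a date comparison, none is.
- **That untimed first-day AZD8871 events split in thirds.** From Protocol Table 4, AZD8871 comes first in sequences A and B, follows Anoro in C and F, and follows placebo in D and E. A reader might infer that one third become non-treatment-emergent, one third go to Anoro and one third to placebo. That ignores the 42-day limit, which leaves attribution open for wash-outs of 43 to 49 days.
- **That 3 × 72 = 216 first-dose days measures the effect.** This counts patient-days if all 72 patients start every period, while the plan allows for about 25% dropout. It is a ceiling on exposure to the rule, not a number of events.

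**What to change.** State in SAP 3.1.1.2 and 3.5.1 that when an AE's observed or imputed start date is the Day 1 dosing date of any period and the time is missing, the event is treated as starting after that period's first dose, unless a recorded stop time precedes the dose. Two ways of doing this work:

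- set the start to the first-dose time plus 1 minute; or
- judge treatment-emergence and period attribution for these events by date, in line with Protocol 9.4.2.

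Setting the start equal to the dose time is not enough, because SAP 3.5.1 requires the event to come after the dose. Keep 00:01 for all other days. SAP 3.5.1 should also say whether date or date-time governs in general, and from which last dose the 42 days run.

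The cost is a sentence or two in each section and a small change to the derivation code. Some Day 1 events that truly began before the dose will be counted as treatment-emergent, which is the conservative direction. With the first option, the computed duration of these events also shortens by about 7 to 11 hours; with the second it does not change.

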3.1.1.3 Imputation for adverse event stop dates

- The following rules will be applied to partial stop dates:
- If only the month and year are specified, then the last day of the month will be used.
- If only the year is specified, then December 31 of the known year will be used.
- If the stop date is completely unknown, the stop date will not be imputed.

Missing or partially missing dates and/or times will be imputed as for the calculation of duration of each AE.

3.1.2 Repeated and unscheduled visits

All repeated and unscheduled measurements will be presented in the listings. Repeated and unscheduled measurements will not be used for statistical analysis or summary tables, unless the repeated measurement was performed due to unreliable values/technical reasons, or the repeated measurement occurred prior to IP administration and is defined as the 'baseline'. The following general rules will apply to all repeated and unscheduled measurements (the below section describes a different approach for spirometry variables):

- For repeated measurements obtained prior to the first dose of IP in each period, the latest reliable value (which may be scheduled or unscheduled) will be used in the calculation of descriptive statistics
- For repeated measurements obtained at the designated Baseline visit, the latest reliable value (which may be scheduled or unscheduled) will be defined as the Baseline in each period. Repeated measurements designated Baseline will be used in descriptive statistics rather than the planned measurement they replace
- For repeated measurements obtained at any time point after the first dose of IP, the first reliable value of any repeated measurements will be used in the calculation of changes from Baseline and for the descriptive statistics.

3.1.2.1 Spirometry variables

For repeated spirometry measurements that are taken on the same day and time as a scheduled visit and time point, the latest nonmissing- result will be used for that visit and time point.

Spirometry data from unscheduled and End of Study visits for patients who discontinue from the study will not be included in the analyses, but all data (from scheduled and unscheduled visits) will be listed.

3.2 Assessment of study population

3.2.1 Demographic and baseline characteristic variables

Demographic characteristics (including country, age, sex, race and ethnicity), baseline characteristics (including height, weight, body mass index [BMI]) and baseline disease characteristics (including COPD history, smoking history, time from diagnosis of COPD to randomisation, time from most recent exacerbation to randomisation, number of exacerbations in previous 12 months and FEV1, FVC variables defined in 4.2.1.2) will be assessed.

3.2.2 Surgical and medical history

Surgical and medical histories will be coded using the latest version of the Medical Dictionary for Regulatory Activities (MedDRA, 21.0 or later).

3.2.3 Prior and concomitant medications

All medications will be classified into anatomical therapeutic chemical (ATC) drug classes using the latest version of the World Health Organization (WHO DD+HD March 2017 or later) Drug Dictionary.

Any medications taken by the patient between 15 days prior to signing the ICF and prior to the first dose date of IP will be considered prior medication. The medications taken by the patient more than 15 days before signing the ICF will be not considered prior medication but will be listed in the general listing of all medications for the patient.

Any medication taken by the patient at any time between the date of the first dose (including the date of the first dose) of IP up to 24h after the last IP administration of each treatment period will be considered concomitant medication.

A medication is considered concomitant for a treatment if the start date of the medication is on or after the date of first dose in that treatment period and prior to or at 24h post last IP intake of the treatment period, or the start date is prior to the date of first dose in that treatment period and a stop date on or after the date of first dose in that treatment period (the medication is ongoing). If a medication is taken over multiple periods of treatment, it will be considered concomitant for all treatments taken in the different periods.

A medication is considered to be taken during wash-out periods if it is taken after 24h of IP intake on Day 14 and before the following treatment period.

Medications that start after one day post the date of last dose of IP during the overall study will not be considered concomitant.

For the purpose of inclusion in prior or concomitant medication summaries, incomplete medication start and stop dates will be imputed as detailed in Section 3.1.1.1.

Medications that start during the follow-up period (ie, that start after one day post the date of the last dose of IP during the study) will only be displayed in listings.

3.2.4 Duration of exposure

Exposure (in days) will be calculated as the treatment duration, from the first dose to the last dose (inclusive), separately for each treatment:

$$\begin{aligned} \text{Treatment duration} \\ &= (\text{last dose date in treatment period} \\ &\quad - \text{first dose date in treatment period}) + 1 \end{aligned}$$

3.2.5 Treatment compliance

Treatment compliance will be calculated separately for each treatment received by a patient.

For all treatments, treatment compliance will be calculated as follows, using the drug accountability data

$$\text{Treatment compliance (\%)} = \frac{\text{Number of puffs taken during treatment period}}{\text{Number of puffs expected during treatment period}} \times 100.$$

3.3 Efficacy variables

3.3.1 Pulmonary function variables

Pulmonary function will be assessed using spirometry performed as follows:

- Pre-dose spirometry is performed before the morning daily dose at Day 1, Day 8, and Day 14 of each treatment period. Two sets of measurements will be performed during

the hour preceding the scheduled morning study drug administration, allowing approximately 45 min between them.

- Trough FEV₁ values are defined as the mean of the values obtained at 23 hours and 23 hours 45 minutes after the morning IP administration on Day 1 and Day 14 (i.e. obtained on Day 2 and Day 15). On Day 8, TFEV₁ value is defined as the mean of the FEV₁ pre-dose values (-1 hour and -15 min).

If one of the two measurements is missing, the non-missing measurement will be used as the trough value.

- Definition above also applies to FVC measurements.
- 4 hour serial spirometry is performed at Day 8 of each treatment period; spirometry will be performed post-dose at 15 minutes, 30 minutes, 1 hour, 2 hours, and 4 hours.
- 8 hour and 24 hour serial spirometry is performed at Day 1 and 14 of each treatment period; spirometry will be performed post-dose at 15 minutes, 30 minutes, 1 hour, 2 hours, 4 hours, 8 hours, 12 hours, 23 hours and 23:45 hours.
- The FEV₁ peak value at a visit is defined as the highest value observed during the 4 hour period immediately following the morning study drug administration at that visit (ie, the maximum value observed at 15 minutes, 30 minutes, 1 hour, 2 hours or 4 hours post-dose).

AUC is defined as the area under the curve.

For t= 4, 8, 12 and 24 AUC is calculated from zero time to t hours (AUC_{0-t}), using the trapezoidal method, divided by the corresponding duration (ie, 4, 8 and 24 hours, respectively) to give the AUC_{0-t/th} values (where t is either 4, 8 or 24) in litres. Non-missing FEV₁, at the following time points are required in order to calculate the normalised AUC_{0-4/4h}: pre-dose; at least one value between 0 and 2 hours and the value at 4 hours post-dose. Similarly, nonmissing- FEV₁ values at the following time points are required in order to calculate the normalised AUC_{0-8/8h}: predose-; at least one value between 0 and 4 hours and the value at 8 hours post-dose. For AUC_{0-24/24h}, nonmissing- FEV₁ values at the following time points are required in order to calculate the normalised AUC_{0-24/24h}: predose-; at least one value between 0 and 8 hours and at least one value post 8 hours post-dose; otherwise the normalised AUC_{0-t/th} will be missing.

Notice that in case that the 23:45 timepoint is missing and only the 23h timepoint is used, the AUC₀₋₂₄ will still be normalized by 24 and AUC_{0-24/24h} computed. The raw AUC will be used (rather than the logs), since the distribution of the FEV₁ data is expected to approximate to a normal distribution.

